## Funder

This study is funded as part of a Wellcome Trust Research Fellowship held by [name].

This protocol describes the **IVM-LICE** study and provides information about procedures for entering participants. The protocol should not be used as a guide for the treatment of other participants; every care was taken in its drafting, but corrections or amendments may be necessary. These will be circulated to investigators in the study, but centres entering participants for the first time are advised to contact the trials centre to confirm they have the most recent version.

Problems relating to this trial should be referred, in the first instance, to the study coordination centre.

This trial will adhere to the principles outlined in the International Conference on Harmonisation Good Clinical Practice (ICH GCP) guidelines, protocol and all applicable local regulations.

# **GLOSSARY OF ABBREVIATIONS**

AAH	Atoifi Adventist Hospital
AE	Adverse Event
SAE	Serious Adverse Event
SUSAR	Serious Unexpected Event

# **KEYWORDS**

Scabies Ivermectin Impetigo Headlice

# **STUDY SUMMARY**

# TITLE A Pilot study evaluating whether treatment of scabies with ivermectin also treats headlice Ivermectin

- **DESIGN** Prospective before and after pilot study
  - **AIMS** Assess the impact of a scabies treatment programme on the prevalence of headlice in the same community.

## **OUTCOME MEASURES** Primary Outcome a) Change in prevalence of headlice between baseline and follow-up

- **POPULATION** Treatment is provided to all eligible residents for scabies. A total population of approximately 150 individuals will be treated
- **ELIGIBILITY** All residents of the Atoifi Hospital Campus are eligible to participate in the study **TREATMENT** *Treatment of scabies:*

Standard treatment in line with guidelines:

Either an oral dose of Ivermectin (200µg/kg) or permethrin cream and

malathion shampoo for those with a contraindication to Ivermectin (WT<15kg,

pregnant or breastfeeding women) given in 2 doses 7-14 days apart.

**DURATION** 3 months

# **1. INTRODUCTION**

## 1.1 BACKGROUND

Scabies and headlice are both common worldwide ectoparaistic infections and scabies in particular is a significant public health problems in the Pacific[1]. Ivermectin is an effective treatment for both conditions. Community mass treatment is now the recognised best approach to treating scabies and household treatment is also commonly used for headlice treatment[2,3]. As ivermectin is used to treat both conditions it would be anticipated that programmatic scabies treatment in a community would also treat head lice. The aim of this small scale pilot study is to evaluate this hypothesis.

#### 1.2 RATIONALE FOR CURRENT STUDY

Ivermectin is known to have a broad range of parasitic activities and is effective at treating many ectoparasitic infections. It is now considered the optimum drug for community treatment of scabies. The drug is also known to be effective for treating headlice but no studies have formally assessed whether community treatment for scabies also reduces headlice prevalence. This study will help us more fully understand any additional benefit on headlice when communities are treated for scabies

# 2. STUDY OBJECTIVES

# **Study Aims:**

Assess the impact of a scabies treatment programme on the prevalence of head lice in the same community.

# **Primary Objective:**

The primary objective is to see whether community treatment for scabies also reduces the prevalence of head lice.

# **3. STUDY DESIGN**

This is a pilot open-label study measuring the impact of scabies treatment on head lice prevalence in the same individuals. In line with recommendations the treatment is provided at the community level.

#### Study Site

This study will be conducted on the campus of Atoifi Adventist Hospital. All staff and their families living on the campus will be invited to participate. Based on input from collaborators at Atoifi campus it is recognised that headlice is a common problem particularly amongst children living on the hospital campus. Treatment will be provided at the level of the community in line with recommendations and best evidence for scabies. All individuals on the campus will be offered treatment and will be invited to participate in the study.

Treatment will be provided at the level of the community in line with recommendations and best evidence for scabies. All individuals will be invited to participate in the study and will be offered treatment.

#### **Community Awareness**

Prior to the study commencing we will engage community leaders on at the hospital campus. A research training workshop will be held at AAH and which will be attended by AAH and other study staff as well as key community leaders. This meeting will provide an opportunity for explanation of the study aims and methodologies and for study staff to answer questions about the study design and implementation.

#### **Eligibility Criteria:**

All residents of the Atoifi Hospital campus will be invited to participate in the study.

#### Inclusion Criteria:

All residents of the selected communities will be invited to participate in the study.

#### **Exclusion Criteria:**

Individuals with a contra-indication to treatment. Individuals not consenting to participate.

## **Duration**

The duration of the study is 3 months. For all participants, there will be a 15 day on-study period which will include two visits by the study team

- Day 1 for baseline medical assessment and delivery treatment
- Day 8-15 for delivery of second dose of treatment

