## Treatment of scabies:

- Day 1 for baseline medical assessment and delivery of ivermectin (or permethrin & malathion when contra-indicated)
- Day 8 for delivery of second dose of ivermectin

An oral dose of Ivermectin ( $200 \mu g/kg$ ).

In individuals with a contra-indication (pregnancy, breast-feeding, weight <15kg) permethrin cream and malathion shampoo will be offered instead.

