## 4.4 WITHDRAWAL CRITERIA

Study participation is voluntary and study participants can withdraw at any time. The number of withdrawals will be recorded and only data collected prior to withdrawal will be included in the analysis. Only data collected prior to withdrawal will be included in the analysis.

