## **Ivermectin**

Ivermectin is an anthelminthic. Ivermectin is metabolized in the liver, and ivermectin and/or its metabolites are excreted almost exclusively in the feces over an estimated 12 days, with less than 1% of the administered dose excreted in the urine. After oral administration, the apparent plasma half-life of ivermectin is approximately 16 hours. Ivermectin is indicated for the treatment of onchocerciasis or river blindness caused by Onchocerca volvulus and for strongyloidiasis caused by Strongyloides stercoralis. The recommended dosage for treatment of scabies is two oral doses designed to provide approximately 200µg of ivermectin per kg of body weight. The same dose is recommended in the Solomon Islands. Ivermectin is available in 3mg tablets.

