#### Contact details for reporting SAEs and SUSARs [contact] / [name] Email: [contact]

# 7. ASSESSMENT AND FOLLOW-UP

#### **Data Collection**

At baseline all individuals will undergo a standardized examination to collect data on the presence of scabies, impetigo and headlice. Following examination individuals will be weighed and directly observed treatment will be dispensed in line with standard treatment guidelines (see below). Individuals will be reexamined at 48 hours to assess immediate killing of head-lice, again at 2 weeks and 3 months.

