# 9. MONITORING

# **9.1 RISK ASSESSMENT**

This is considered a low risk study.

All the drugs being used are being prescribed for routine indications and have well established safety profiles. As such only passive monitoring for adverse events will be undertaken during the study.

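### Serious adverse events are the only safety data, yet they are collected passively and none of the three planned re-examinations is described as asking about them

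*Combined protocol and SAP*

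**What the plan says.** **Period and visits.** The Duration section of the protocol puts the study at 3 months and then says: "For all participants, there will be a 15 day on-study period which will include two visits by the study team". The second of those visits is given as "Day 8-15 for delivery of second dose of treatment". The Study Summary agrees on the interval ("given in 2 doses 7-14 days apart"), but the section on treatment of scabies has "Day 8 for delivery of second dose of ivermectin", and section 9.3 also places the second-treatment site visit on Day 8.

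**Examinations.** Section 7 (Data Collection) has more contacts than two: "Individuals will be reexamined at 48 hours to assess immediate killing of head-lice, again at 2 weeks and 3 months".

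**Safety data.** Section 6.3.1 limits collection to SAEs and SUSARs. Section 6.3.2 asks for a report within 24 hours of the site learning of an event and gives no closing date for collection. Section 9.1 describes the method: "As such only passive monitoring for adverse events will be undertaken during the study". Section 9.3 has adverse event forms reviewed at each visit after baseline, up to month 3.

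**The concern.** With SAEs and SUSARs as the only safety information, whatever the study says about harm depends on how those events reach the record. Under passive capture an event is recorded only if someone brings it to the site. The protocol brings participants back three times after baseline, but describes those contacts in terms of skin and head-lice findings and does not say that anyone asks about a death in the household, a hospital admission or another serious illness.

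The different schedules make this worse. A reader of the Duration section sees a participant period that can close on the day of the second dose. A reader of sections 7 and 9.3 sees contact until month 3. Site staff have no stated end date for SAE collection to settle the matter.

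What is at stake is the meaning of a null safety finding. If no SAEs are reported, the reader cannot tell absence of events from absence of reports.

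**Working it through.** This is a matter of counting days and comparing sections. No power or sample-size figure is involved.

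**1. Reproduce the 15-day figure.** Inputs: first dose on Day 1, and a second dose 7 to 14 days later (Study Summary).
- Earliest second dose: 1 + 7 = Day 8. Latest: 1 + 14 = Day 15. This matches the window in the Duration section.
- Length of Day 1 to Day 15 inclusive: 15 − 1 + 1 = 15 days. The stated figure is reproduced, and its last day is the latest permitted second-dose day.

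**2. Set the schedules side by side.**

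| Section | Contacts |
|---|---|
| Duration | Day 1; Day 8 to 15 (two visits) |
| Treatment of scabies | Day 1; Day 8 |
| 7, Data Collection | baseline; 48 hours; 2 weeks; 3 months (four examinations) |
| 9.3 | Day 1; Day 8; month 3 (three site visits) |

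Two visits within 15 days cannot hold four examinations reaching to 3 months. These sections need reconciling.

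**3. Look for a safety enquiry at each contact.**
- Baseline: examination for scabies, impetigo and headlice, then weighing and treatment.
- 48 hours: killing of head lice.
- 2 weeks and 3 months: re-examination, with no further content stated.
- Second dose: delivery of treatment.
- Section 9.3: review of adverse event forms. This checks what has been written down. It does not say that participants are asked.

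Re-examinations described as including a question on serious events: 0 of 3.

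**4. Find the gap after the second dose.** Assumptions: the examination times in section 7 run from Day 1, and month 3 is about Day 90.
- The 48-hour examination falls on Day 1 + 2 = Day 3, and the 2-week examination on about Day 14 or 15.
- Second dose on Day 8: the 2-week examination comes 14 − 8 = 6 to 15 − 8 = 7 days later.
- Second dose on Day 15: the 2-week examination falls on the dosing day or the day before. The next scheduled contact is month 3, 90 − 15 = 75 days later.
- If the 2-week examination were instead counted from the second dose, it would fall on Day 15 + 14 = Day 29 and the long gap would close. The protocol does not say this, so the 75 days is a possibility and not a certainty.

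**5. Check how far monitoring extends.** Section 9.1 applies passive monitoring for the duration of the study. The Duration section and section 7.2 both put that at 3 months. The reporting rule in section 6.3.2 has no Day 15 cut-off, and section 9.3 reviews adverse event forms at month 3. Nominal coverage therefore reaches month 3 whatever the day of the second dose.

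**The case against.** The strongest reply is that passive, SAE-only monitoring is a deliberate and reasoned choice. The drugs are used for established indications, their safety profiles are well known, and sections 6.3.1, 9.1 and 11 give this reasoning openly. Participants are hospital staff and their families living on the hospital campus, where a death or admission would plausibly come to the site's notice. All of this stands, and it is why the point is of low priority. It does not remove the observation that a better method is available at visits the plan already contains.

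Three stronger readings are tempting, and the documents do not support them.

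- **That the time after the second dose goes unobserved.** A reader might infer this from a 15-day period ending on a Day 15 dose. No section equates that period with the SAE collection period, and step 5 shows monitoring nominally running to month 3.
- **That a 12-day safety window is missed.** Section 5.1 says that ivermectin is "excreted almost exclusively in the feces over an estimated 12 days". Counting 12 days from the second dose gives days 9 to 20 for a Day 8 dose (5 of them after Day 15) and days 16 to 27 for a Day 15 dose (all 12 after Day 15). But the figure describes faecal excretion and is not offered as a safety-observation period. The same section gives a plasma half-life of about 16 hours, and five half-lives are 5 × 16 = 80 hours, about 3.3 days. The figure does not apply to people given permethrin and malathion. In every case the 12 days end 90 − 20 = 70 to 90 − 27 = 63 days before month 3, well inside the study.
- **That withdrawn participants' SAEs are dropped.** Section 4.4 says "only data collected prior to withdrawal will be included in the analysis". The only outcome defined for analysis is the change in headlice prevalence, no safety analysis is specified, and the reporting duty in section 6.3.2 has no exemption for people who withdraw. The wording does not remove SAEs from a safety result.

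**Conclusion.** The point holds in a limited form. The only safety data in the study depend on passive reporting, and none of the three planned re-examinations is described as asking about serious events. Up to about 150 residents are affected. No enquiry is guaranteed after either dose. For a second dose on Day 15 the next scheduled contact may be month 3, about 75 days on, assuming that the examinations run from Day 1 and that month 3 is Day 90. With a Day 8 dose, the 2-week examination follows 6 to 7 days later, but it too carries no stated safety question.

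Separately, the two-visit, 15-day on-study period contradicts the contacts in sections 7 and 9.3, and the second-dose timing differs between sections (Day 8 against Day 8 to 15). Section 6.3.2 states no end to SAE collection, although month 3 can be inferred from other sections. None of this shows that safety data would be lost. It shows that a finding of no SAEs would be weaker than it need be. Low priority, as an inexpensive improvement.

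**What to change.** - **Section 9.1:** replace passive-only monitoring with one scripted question on death, hospital admission or other serious illness, asked and recorded (including a negative answer) at the 48-hour, 2-week and 3-month examinations already planned.
- **Section 6.3.2:** state that SAE collection runs to the month-3 visit for treated participants, including those who withdraw and consent to this.
- **Duration section:** reconcile the 15-day, two-visit period with the contacts in sections 7 and 9.3, make the second-dose timing agree across sections, and say from which day the section 7 examinations are counted. Which schedule is intended is for the sponsor to state.

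The cost is one extra form item at each of three existing visits, a few sentences of protocol text, and probably a few more unrelated SAEs to record. No new visits or staff are needed, and the point calls for no change of dose.

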## Treatment

No investigational medications or indications are being assessed. All individuals will receive standard treatment for scabies.

## Treatment of scabies:

- Day 1 for baseline medical assessment and delivery of ivermectin (or permethrin & malathion when contra-indicated)
- Day 8 for delivery of second dose of ivermectin

An oral dose of Ivermectin ( $200 \mu g/kg$ ).

In individuals with a contra-indication (pregnancy, breast-feeding, weight <15kg) permethrin cream and malathion shampoo will be offered instead.

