## **5.5** Preparation and labelling of IMP

For participants receiving ivermectin, the dose will be determined according to body weight and treatment will be administered under direct supervision of the study team. Drug administration will be recorded in a standardized record form.

Participants assigned to permethrin (due to contra-indication to ivermectin) will receive a tube of cream and will be asked apply the cream from neck to toes before they leave the clinic and under supervision of a study nurse, and leave it on for a minimum of 8 hours, maximum 24 hours if possible. For children aged 2 months or less, cream will applied for a maximum of 4 hours.

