#### **5.6** Dosage schedules/modifications

In line with standard treatment the dosing of Ivermectin will use the following weight bands

Permethrin will be used instead of Ivermecitn in the following circumstances

- Pregnancy
- Breastfeeding
- Child <6 months age
- Child <15kg

Where permethrin is indicated the following standard dosing protocol will be used:

- Full tube for adults.
- Half tube for children.
- Apply to whole body and leave on for 1 day before washing off

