# **5.8** Concomitant medication

Individuals receiving Warfarin may not receive treatment with Ivermectin due to potential interactions. No individuals outside of the capital of the Solomon Islands (Honiara) are receiving Warfarin due to a lack of INR monitoring facilities and therefore it is not anticipated that any individuals in the study will be receiving a contra-indicated concomitant medication. Permethrin will be offered if a patient taking warfarin was identified.

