## **5.9** Trial restrictions

There are no trial restrictions.

As noted above pregnant and breast feeding women and children <15kg will be offered permethrin rather than ivermectin but will still be allowed to participate in the study.

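### The protocol leaves open whether residents who cannot take ivermectin get any product on the head, although head lice is the only outcome

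*Combined protocol and SAP*

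**What the plan says.** **Product.** The study summary pairs permethrin cream with "malathion shampoo for those with a contraindication to Ivermectin (WT<15kg", and extends this to pregnant and breastfeeding women. Section 3 (Treatment of scabies) says the same twice: in the schedule, "Day 1 for baseline medical assessment and delivery of ivermectin (or permethrin & malathion when contra-indicated", and then in full, "In individuals with a contra-indication (pregnancy, breast-feeding, weight <15kg) permethrin cream and malathion shampoo will be offered instead".

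Section 5 (Trial medication) names permethrin alone. The weight table in 5.4 puts permethrin cream in the row for under 15 kg. Section 5.6 lists when permethrin replaces ivermectin. Section 5.8 says "Permethrin will be offered if a patient taking warfarin was identified". Section 5.9 says "pregnant and breast feeding women and children <15kg will be offered permethrin rather than ivermectin but will still be allowed to participate in the study".

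**Area of application.** Section 5.5 has participants "apply the cream from neck to toes before they leave the clinic and under supervision of a study nurse". Section 5.6 says "Apply to whole body and leave on for 1 day before washing off" and does not mention the head. The permethrin product paragraph in section 5 uses both descriptions in one sentence.

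**Who is in the study.** The exclusion criteria in section 3 include a contra-indication to treatment. Those in section 4.3 do not, and section 5.9 expressly keeps these residents in.

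**Outcome.** Sections 3.1 and 8 give one outcome, the change in head-lice prevalence from baseline to follow-up, with no separation by treatment received.

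**The concern.** The question is whether treating a community for scabies also reduces head lice. For ivermectin recipients the exposure is clear: an oral drug. For residents who cannot take it, the exposure of the head depends on which section the dispensing staff follow. Under the summary and section 3 they receive a shampoo. Under section 5.5 they receive a cream from the neck down and nothing on the head.

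The two readings pull the primary result in opposite directions. With no head product, the group dilutes any effect of ivermectin. With a shampoo, lice cleared by a head treatment are counted in the same overall figure and could be credited to ivermectin. The group may also matter for lice: section 3 (Study Site) says head lice are common particularly among children, and children under 15 kg fall in this group. The protocol does not, however, give a lice prevalence for those children.

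**Working it through.** **Step 1: the texts side by side.**

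| Place | Replacement product | Where applied |
|---|---|---|
| Study summary; section 3, Treatment of scabies | permethrin and malathion shampoo | not stated, but a shampoo goes on the head |
| Section 5, permethrin paragraph | permethrin | all over the body, and neck to toe |
| 5.4, weight table | permethrin | not stated |
| 5.5 | permethrin | neck to toes |
| 5.6 | permethrin | whole body, head not mentioned |
| 5.8 (warfarin), 5.9 | permethrin | not stated |

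Malathion has no product description, legal status, supply or administration instruction in section 5, and section 4.1 also names only ivermectin and permethrin. The available text of section 5 has gaps (5.7 starts mid-sentence and there is no 5.3), so this absence is a statement about the text that can be read.

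**Step 2: what the difference could do to the result.** Inputs from the sample-size paragraphs (sections 3.1 and 8): baseline prevalence 25%, follow-up prevalence 10%. The share *s* of participants on the alternative is not given; 10%, 20% and 30% are assumed. Ivermectin recipients are assumed to reach the planned 10%. The alternative group ends at prevalence *p*:

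overall follow-up prevalence = (1 − *s*) × 10% + *s* × *p*

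With *s* = 0 this returns the plan's own 10%, a fall of 25 − 10 = 15 points.

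| *s* | Nothing on the head, *p* = 25% | Head product, *p* = 0% to 10% | Gap in points |
|---|---|---|---|
| 10% | 9 + 2.5 = 11.5% | 9% to 10% | 1.5 to 2.5 |
| 20% | 8 + 5 = 13.0% | 8% to 10% | 3 to 5 |
| 30% | 7 + 7.5 = 14.5% | 7% to 10% | 4.5 to 7.5 |

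At a 20% share the observed fall is 25 − 13 = 12 points in one case and 15 to 17 points in the other.

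**Step 3: numbers of people.** Taking 80% enrolment of 150 gives 120 participants. A 20% share is then 24 people, about 24 × 0.25 = 6 of them infested at baseline. At shares of 10% and 30% the counts are 12 people (3 infested) and 36 people (9 infested).

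The stated sample size of 150 cannot be reproduced, because no significance level, power or test is given. Nothing here depends on it beyond the head counts in step 3.

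**The case against.** The best defence is that the texts can be read together. Malathion is named three times as an addition to permethrin, and no section withholds it. Section 5 may simply be saying what replaces ivermectin as the scabies drug, with malathion left for the head. That stands in part: the conflict is by omission. It does not remove the problem, because staff working from section 5 as written would give nothing for the head.

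Four stronger readings are tempting and go too far.

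- *Three distinct interventions.* A reader might infer that section 5.6 puts permethrin cream on the head. It does not mention the head, and the product paragraph uses both area descriptions together, so this is only a possible reading.
- *Practice varied and cannot be recovered.* This is one campus of about 150 people, treated by the study team. Section 5.4 requires a dispensing log that can be checked against study records, and section 5.5 a standardised administration form. Variation between staff is not documented, and the product given should be recoverable. What is not provided for is a record of whether anything was applied to the head.
- *The primary result would be uninterpretable.* The figures above rest on an assumed share and compare everyone with no one receiving a head product. Holding the group at 25% also ignores any fall in transmission once neighbours are treated. And if the exclusion in section 3 were applied, the group would not be in the analysis.
- *Clearance after a head product should not count.* The stated aim is the effect of a treatment programme on community prevalence, and the summary lists malathion within standard treatment. Discounting those clearances would change what is estimated, and counting cleared people as infested would bias prevalence upwards.

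**Conclusion.** The point holds as an unresolved inconsistency about product, area of application and eligibility for one group of residents. It needs settling because whether the head is treated bears directly on the only outcome. It does not show that malathion will be withheld, that practice will differ between staff, or that the primary result is lost.

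Its size cannot be computed from the documents. At an assumed 20% share, the choice of text moves overall follow-up prevalence between 13% and 8–10%, which is 3 to 5 points set against a planned 15-point fall. This assumes that ivermectin recipients go from 25% to 10%, that the group starts at 25%, and that it is kept in the analysis. The no-head-product figure is a bounding case.

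**What to change.** Before the first treatment day:

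1. Reconcile the study summary and section 3 (Treatment of scabies) with the permethrin paragraph in section 5 and with 5.4, 5.5, 5.6, 5.8 and 5.9, so that one product list and one area of application cover every resident who cannot take ivermectin, including a warfarin user. Reconcile the section 3 exclusion criteria with section 5.9 at the same time. Which regimen is right is for the investigators; no view is taken here.
2. On the existing administration form, record at each treatment day the product given and whether any was applied to the head.
3. Keep the overall change in community prevalence as the primary outcome. In addition, report the change separately for ivermectin recipients and for residents given the alternative, the latter split by whether a head product was applied. Clearance after a head-applied product is then not attributed to ivermectin.

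The cost is protocol wording, a tick box and one extra tabulation, with no added visits or participants. The subgroup will be small (about 24 people at a 20% share), so that table should be descriptive.
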